7.9 Treatment Discontinuation

7.9.1 Criteria for Treatment Discontinuation

SL-401 treatment may be discontinued for any of the following reasons:

- Patient withdrawal of consent.
- Occurrence of unacceptable toxicity, including DLT.
- SL-401 related anaphylaxis or ≥ grade 3 hypersensitivity reaction
- Disease recurrence/progression.
- Intercurrent illness that prevents further administration of SL-401.
- Patient non-compliance.
- Occurrence of pregnancy.
- Completion of 6 cycles of treatment.
- Investigator's decision.

The reason for SL-401 discontinuation and the date of discontinuation should be recorded in the electronic case report form (eCRF).

7.9.2 Procedures and Follow-up after Treatment Discontinuation

The evaluation during which the Investigator determines that SL-401 or SL-401/POM/DEX will be discontinued should be considered the EOT Evaluation; all tests and procedures for the EOT Evaluation are listed in Table 13. In addition, patients should be followed for a minimum of 30 days after the last dose of SL-401 or SL-401/POM/DEX for assessment of AEs (including potential new AEs and potential change/resolution of existing AEs).

Patients who discontinue therapy for reasons other than progression will be followed every month until progression of disease or initiation of subsequent therapy. Disease assessments should continue to be performed as described in Table 13, until there is evidence of relapsed or progressive disease in the judgment of the Investigator. Following progression, either on or off therapy, patients will be followed for survival every 3 months for up to 1 year.

If the patient discontinues SL-401 treatment and also withdraws consent for collection of future information, no further evaluations should be performed and no additional data should be collected as part of the study. The Sponsor will only retain and use any data collected before withdrawal of consent.

Consult Section 6.4 for recommendations concerning ongoing follow-up of patients alive with or without evidence of disease progression at the time of Study Completion/assessment of primary and critical secondary endpoints.

8 Study Procedures

8.1 Patient Selection

Patients with RRMM who have previously received at least 2 lines of therapy for their disease and who otherwise meet the inclusion/exclusion criteria will be recruited for enrollment into the study. Patients will be advised of the clinical protocol by the Investigator. If the patient is interested and is potentially eligible for participation in the study, he/she will be provided with the informed consent form (ICF) to review and sign. The ICF includes a detailed explanation of the study design and the potential risks and benefits of treatment. Patients who agree to participate in the study will be provided with a copy of the signed consent form; the original signed consent document will be filed in the patient's medical record. Only eligible and consenting patients will be entered into the study.

Patients will be screened by the Investigator or study nurse/coordinator prior to study entry. All patients enrolled on the study will be entered into a patient registration log at each site.

Original screening records

and source documents should be kept for all patients, including those who fail to meet the patient eligibility requirements and any completed eCRFs should be retained for monitoring and auditing. Each patient's data obtained from subsequent evaluations should be recorded and evaluated in the source documents and eCRF. Prior to treatment, the Investigator will re-confirm patient eligibility criteria and assignment of the correct patient study number.

8.2 Medical History

Medical history includes current and past medical conditions and smoking history, date of MM diagnosis, prior MM treatment, response to prior treatment, and date of relapse, if applicable. Information concerning any prior malignant diagnoses with particular focus on cytotoxic therapies received for prior malignancies (i.e., dates/duration of anthracycline for prior breast cancer) is to be collected whenever feasible.

8.3 Prior and Concomitant Medication

Medications taken within 28 days prior to screening and throughout the study are to be collected and recorded.

8.4 ECOG Performance Status

See Section 15.1 for a scoring guide.

8.5 Physical Examination

Physical examination includes evaluation by body system, weight, and height (at screening only), evaluation for extramedullary plasmacytomas and neurologic assessment.

8.6 Vital Signs

Vital signs include temperature, HR, RR, pulse oximetry, and BP. Collection should occur after the patient has been sitting for 3-5 minutes. See Section 7.7.2.2 for collection schedule.

8.7 Electrocardiograms

All patients will have a 12-lead ECG performed at the screening visit, Day 1 of each cycle and at the EOT visit.

8.8 Clinical Laboratory Tests

The following assessments should be done per the visit schedule and processed by the local laboratory:

- Hematology: Minimally, scheduled hematology collections should include white blood cell count, differential white cell count (lymphocytes, monocytes, basophils, eosinophils, neutrophils), red blood cell count, hematocrit, hemoglobin and platelet count.
- Serum albumin: May be a component of the serum chemistry panel. See Section 7.2.2 for administration of albumin if serum albumin decreases to < 3 g/dL during treatment days or in the immediate post-treatment period.
- Serum electrolytes and chemistry: Chemistry includes: glucose (fasting at baseline), albumin, total protein, AST, ALT, bilirubin (total and direct), alkaline phosphatase (AP), LDH, CPK, sodium, potassium, chloride, bicarbonate/carbon dioxide, calcium, magnesium, phosphate, uric acid, blood urea nitrogen (BUN), serum creatinine and estimated creatinine clearance (Cockroft-Gault formula; see Appendix 15.7). Albumin, transaminases (AST/ALT) and creatinine must be evaluated prior to each SL-401 dose.
- Coagulation parameters: PT and/or INR, aPTT.
- Urinalysis: Appearance, color, pH, specific gravity, ketones, leukocytes, protein, glucose, bilirubin, urobilinogen, and occult blood.

8.9 Urine or Serum Pregnancy Test

Urine or serum pregnancy tests must be completed prior to the Run-in Cycle of Sl-401 and urine or serum pregnancy tests of at least 50 mIU/mL must be performed for females of child bearing potential within 7 to 10 days and again within 24 hours of initiation of POM therapy. Repeat pregnancy test every week for the first 4 weeks and then every 28 days while on therapy and during interruptions in therapy and 28 days following discontinuation of POM Women with irregular menstruation must have pregnancy testing every 14 days while on therapy and during interruptions and 14 and 28 days after discontinuation of POM. All patients enrolled into this study must be registered in and must comply with all requirements of the POMALYST REMS™ program.

8.10 Tumor Assessments

Secondary efficacy endpoints will include: PFS; PFS-6; ORR (CR + VGPR + PR) and clinical benefit rate (CR + VGPR + PR + MR) based on IMWG defined response criteria, as well as the DOR; and OR. Tumor assessments are to be done prior to the start each cycle and may be performed within the 7 days prior to Day 1 of a new cycle.

Efficacy assessment parameters will include:

- M-protein determination using both of the following procedures:
 - Serum protein electrophoresis (SPEP) and serum protein immunofixation with quantitative immunoglobulins; and
 - Urine protein electrophoresis (UPEP) and urine protein immunofixation (all using the same 24-hour urine collection)
- Serum FLC
- Bone marrow aspirate to quantify percent MM cell involvement
- Plasmacytoma evaluation: positron emission tomography/computed tomography (PET/CT) scan or magnetic resonance imaging (MRI) and or physical examination, as clinically indicated
- Skeletal survey
- Serum β₂ microglobulin (at baseline only)
- Cytogenetics/fluorescence in situ hybridization (FISH) on BM aspirate (at baseline only)

8.11 Translational/Correlative Research Assessments

Additional BM and blood samples (beyond what is required for assessment of response/progression) will be obtained for correlative research to identify mechanism(s) of response/resistance to SL-401 therapy as follows:

- Bone marrow aspirate and biopsy will be obtained prior to, during and following therapy in order to characterize the expression of IL-3R/CD123 (and other potentially relevant markers) on MM cells and associated cell populations using IHC and flow cytometry.
- Peripheral blood (whole blood) for MM and other relevant mononuclear cells will be
 obtained at baseline, Day 1 of Cycles 2, 4 and 6 and at EOT in order to characterize the
 expression of IL-3R/CD123 (and other potentially relevant markers) on MM cells and
 associated cell populations using IHC and flow cytometry.

 Peripheral blood (serum and plasma) will be obtained at baseline, Day 1 of Cycles 2, 4 and 6 and at EOT to evaluate levels of circulating cytokines (i.e., IL-3 and others) relevant to MM cell interactions with accessory (non-neoplastic) cells.

Specimen Collection and Handling Instructions:

- BM aspirate (10-15 mL in heparinized syringe; smaller amounts if 10 cc not available)
- Peripheral blood: 4 tubes total
- (3 × 10 mL green top tubes, 2 for whole blood; 1 for plasma)
- $(1 \times 10 \text{ mL red top/serum-separating tube for serum})$

Labeling and shipping for all samples

Bone marrow and peripheral blood samples will be immediately sent to: [name] laboratory, as follows:

[name].

Label all specimens with the following:

- Subject initials
- ii. Subject study number (will include protocol number)
- Visit at which sample was drawn (i.e., C1D4)
- Date sample drawn (i.e., mm/dd/yyyy)
- v. Time sample drawn (24 hour clock)
- Sample type (e.g., plasma, serum, BM cells, tumor cells)

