3.5.5 Pomalidomide

Pomalidomide (POM), an analog of thalidomide, is an Immunomodulatory Drug (IMiD) with antineoplastic activity. In *in vitro* cellular assays, POM inhibits proliferation and induces apoptosis of hematopoietic tumor cells. Additionally, POM has been demonstrated to inhibit the proliferation of lenalidomide-resistant MM cell lines and synergizes with dexamethasone (DEX) in both lenalidomide-sensitive and lenalidomide-resistant cell lines to induce tumor cell apoptosis. POM has also been shown to enhance T cell- and natural killer cell-mediated immunity and inhibit production of pro-inflammatory cytokines (e.g., tumor necrosis factor-α and IL-6) by monocytes.

POM is indicated for patients with MM who have received at least 2 prior therapies including lenalidomide and bortezomib and have demonstrated disease progression on or within 60 days of completion of the last therapy.

A phase 2 study randomized 221 patients to received either POM and DEX (n = 113) or POM alone (n = 108) (Richardson 2014). The efficacy of POM was enhanced by the addition of DEX; with a median follow-up of 14.2 months, median progression-free survival (PFS) was 4.2 and 2.7 months and the overall response rate (ORR) was 33% and 18% (P = 0.013) respectively. In a subsequent Phase 3 study of patients with advanced MM who had exhausted bortezomib and lenalidomide treatment the benefits of POM and low-dose DEX were further demonstrated in terms of PFS (4.0 months) and OS (12.7 months) versus high-dose DEX, the standard of supportive care (PFS 1.9 months and OS 8.1 months) (San Miguel 2013). POM and low-dose DEX are generally well tolerated, and provide an important new treatment option for relapsed/refractory multiple myeloma (RRMM) patients who have received multiple prior therapies. However, all patients ultimately progress with no further treatment options or die from their disease. Further studies are warranted to evaluate the use of POM in combination with other novel agents to improve upon these outcomes.

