6.2.1 Phase 1: Dose Escalation

Run-In Cycle: SL-401 will be evaluated at doses of 7, 9, or 12 μg/kg/day, for 5 consecutive days (Days 1-5; with postponement as required by adverse events such that 5 doses over 10 days is permitted) as single agent during an initial Run-in Cycle. Upon completion of the Run-in Cycle patients will be evaluated for safety and response.

- Patients who do not experience a DLT during the Run-in Cycle will have POM/DEX added to their regimen at the assigned cohort dose.
- Patients who experience a DLT during the Run-in Cycle will be discontinued from study.

Table 7 details the SL-401/POM/DEX dose levels, beginning with dose level 1 to be evaluated.

Table 7: Dose Levels to be Evaluated

Dose Level	DLT EVALUTION PERIOD = RUN IN CYCLE and CYCLE 1				
	Run-In Cycle	Combination therapy Cycles 1 - 6			
	SL-401(IV) Daily on Days 1 – 5	SL-401(IV) Daily on Days 1 – 5	POM (oral) Daily on Days 1 – 21	DEX (oral) on Days 1, 8, 15 and 22	
-1	5 μg/kg	5 μg/kg	4 mg	40 mg	
1	7 μg/kg	7 μg/kg	4 mg	40 mg	
2	9 μg/kg	9 μg/kg	4 mg	40 mg	
3	12 μg/kg	12 μg/kg	4 mg	40 mg	

Cohorts of 3-6 patients will be treated at each dose level. All patients within a cohort must complete the Run-in Cycle and the first cycle of combination therapy (Cycle 1) before patients can be enrolled into the subsequent cohort of SL-401 (single agent) at the next higher dose. No intra-patient dose escalation is allowed. The first cohort of patients will receive SL-401 single agent at a dose of 7 µg/kg/day followed by SL-401 with POM/DEX. After all patients in this cohort complete the Cycle 1 of therapy, the dose for the second cohort of patients will increase to 9 µg/kg/day, conditional on the DLT rules described below. Similarly, after all patients in the second cohort complete Cycle 1 of therapy, the dose for the third cohort of patients will increase to 12 µg/kg/day, conditional on the DLT rules described below.

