9.3 Cycles 1 through 6 combination therapy (Phase 1 and 2)

- 9.3.1 Days 1 5 (Up to Day 10 if Infusion(s) Held): Pre-infusion
 - Inpatient admission or treatment at a suitable outpatient facility.
 - Physical examination (complete physical examination on Day 1; symptom-directed on other days, as warranted).
 - ECOG performance status (Day 1 only).
 - Vital signs and weight.
 - 12-lead ECG (Day 1 only of each cycle).
 - Pregnancy test for FCBP within 24 hours prior to initiation of POM.
 - Clinical laboratory tests: hematology and serum chemistry (Day 1 of each cycle).
 - PT or INR/aPTT.
 - Urinalysis (Day 1 only of each cycle).
 - Extramedullary disease evaluation according to IMWG criteria (if needed to confirm response).
 - BM aspiration (if needed to confirm response).
 - Collection of blood (whole blood, serum, plasma) for correlative studies; Phase 1: Day 1
 of Cycles 1, 3 and 5. Phase 2: Day 1 of Cycles 2, 4, and 6.
 - Collection of peripheral blood for immunogenicity (serum) If infusions are held (postponed) for any reason, an immunogenicity sample must be collected within 3 ± 3 days after completion of the last SL-401 infusion for the cycle.
 - MM-specific laboratory tests (Day 1 only a -7 day window is permitted for scheduling).
 - PK sampling; phase 1 only (Cycle 2 only, infusions 1 and 5) prior to and following infusion.
 - Diphenhydramine 50 mg IV 60 minutes prior to infusion.
 - Acetaminophen 650 mg PO 60 minutes prior to infusion.

- Methylprednisolone 50 mg IV (or an equivalent dose of another corticosteroid)
 60 minutes prior to infusion.
- Ranitidine 50 mg IV (or an equivalent doses of another H₂-histamine antagonist)
 60 minutes prior to infusion. Days 1 5 (up to Day 10 if infusion(s) held): infusion 15-minute IV infusion of SL-401 at required dose.
- POM administration (Days 1 21) (POM to be administered 4 6 hours post infusion on the day of infusion 1 and 5 of Cycle 2).
- DEX administration (Days 1, 8, 15 and 22) (DEX to be administered 4 6 hours post infusion on the day of infusion 1 of Cycle 2).
- Vital signs: immediately after completion of infusion and 30, 60, and 240 minutes postinfusion.
- Monitoring for at least 4 hours.
- AE and SAE monitoring. Concomitant medication assessment.

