- k. Bone Marrow Aspiration: Bone marrow aspiration for cytogenetic analysis both by FISH and standard karyotyping, and morphologic evaluation including assessment of plasma cell percentage is required at screening/baseline (within 21 days prior to study drug administration. Bone marrow aspirate should be repeated if CR or stringent complete response (sCR) is suspected to confirm achievement of response according to IMWG criteria, and at End of therapy. Additional BM aspirate material (10-15cc if feasible) and biopsy for correlative studies are to be collected at baseline and any time a specimen is obtained to confirm response.
- Peripheral blood for correlative studies should be obtained at baseline, for phase 1 Day 1 of Cycles 1, 3, and 5 and for phase 2 on Day 1 of Cycles 2, 4, and 6 and at EOT for all patients. Four 10 mL tubes in total (3 green top, 1 red top/serum separator tube). Whole blood will be evaluated for circulating MM/plasma cells (and other mononuclear cells of interest); serum and plasma will be for evaluated for potentially relevant circulating cytokines, and surrogate markers of osteolytic activity.
- m. Myeloma-specific laboratory tests: β2 Microglobulin (at baseline only), serum and 24-hour urine immunoelectrophoresis, serum immunoglobulin assay, serum/urine immunofixation and serum FLC with kappa/lambda ratio to be performed at baseline, every cycle prior to study drug administration thereafter and at end of treatment (if last tests were > 4 weeks) and for patients who discontinue therapy for reasons other than disease progression. Myeloma laboratory tests will be repeated every month until disease progression or initiation of subsequent therapy. Response assessment will be done at the beginning of every cycle. Following pre-treatment evaluations on Day 1 of the first cycle evaluations may be performed on Day 1 of a subsequent cycle or during the 7 days prior to Day 1 of the Cycle as needed for scheduling. (Note that an evaluation performed during the final week of Cycle 1 should nonetheless be recorded as the evaluation for the beginning of Cycle 2, with similar assignments for subsequent cycles).

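### Section 8.11 puts correlative blood at Cycles 2, 4 and 6 for everyone, contradicting Section 9.3.1 and Table 13 for phase 1; following it loses the one dedicated draw between the SL-401 Run-in and POM/DEX

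*Protocol*

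**What the plan says.** **Blood.** Section 8.11 lists two kinds of correlative blood, with the same timing and no split by phase. Whole blood is to be "obtained at baseline, Day 1 of Cycles 2, 4 and 6 and at EOT in order to characterize the" expression of CD123 and related markers. For cytokines, "Peripheral blood (serum and plasma) will be obtained at baseline, Day 1 of Cycles 2, 4 and 6 and at EOT".

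Section 9.3.1, the visit-by-visit list for the combination cycles, places the phase 1 draws on Day 1 "of Cycles 1, 3 and 5. Phase 2: Day 1 of Cycles 2, 4, and 6". Table 13 note l agrees: "for phase 1 Day 1 of Cycles 1, 3, and 5 and for phase 2 on Day 1 of Cycles 2, 4, and 6", in addition to baseline and EOT.

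**Treatment sequence.** In phase 1, SL-401 is given alone in a Run-in Cycle. Section 6.2.1 then states: "Patients who do not experience a DLT during the Run-in Cycle will have POM/DEX" added. Phase 2 has no Run-in (Section 6.2.4).

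**Marrow.** Section 8.11 says: "Bone marrow aspirate and biopsy will be obtained prior to, during and following therapy". Table 13 note k says that extra aspirate and biopsy "for correlative studies are to be collected at baseline and any time a specimen is obtained to confirm response". The same note requires a repeat aspirate when CR or sCR is suspected and again at the end of therapy, without assigning correlative material to that last specimen. The synopsis allows aspirate left over from tumor assessment to be used for translational work, with no restriction to responders.

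**The concern.** The exploratory objectives (Section 4.3) ask for treatment effects on CD123 expression, plasmacytoid dendritic cells and circulating cytokines before, during and after therapy. The Run-in is the only period in which patients receive SL-401 without POM/DEX. Pomalidomide is itself expected to move some of these markers: Section 3.5.5 says that it has been shown to "inhibit production of pro-inflammatory cytokines (e.g., tumor necrosis factor-α and IL-6) by monocytes". A first on-treatment sample taken after a combination cycle therefore cannot separate the contribution of SL-401 from that of POM/DEX.

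The Cycle 1 Day 1 draw in phase 1 falls at the end of that period. Whether it is taken depends on which section a site follows. Section 8.11 also holds the tube, labelling and shipping instructions, so sites have a practical reason to work from it. A missed draw cannot be recovered later.

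For marrow, if note k is read as a complete list, post-baseline correlative material would come only from specimens taken to confirm response. A fall in dendritic cells could then not be told apart from selection of responding patients.

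**Working it through.** The protocol states no figure on this point, so the check is a comparison of schedules and a count of cycles.

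**Draws per patient who completes six combination cycles**
- Section 8.11: baseline + 3 (Cycles 2, 4, 6) + EOT = 5.
- Section 9.3.1 and note l, phase 1: baseline + 3 (Cycles 1, 3, 5) + EOT = 5.
- Section 9.3.1 and note l, phase 2: baseline + 3 (Cycles 2, 4, 6) + EOT = 5.

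**Exposure before a Day 1 draw in cycle c**
- Phase 1, SL-401 cycles completed: 1 (Run-in) + (c − 1) = c.
- Phase 2, SL-401 cycles completed: c − 1.
- Both phases, POM/DEX cycles completed: c − 1.

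| Schedule | Phase | Draw cycles | SL-401 cycles completed | POM/DEX cycles completed |
|---|---|---|---|---|
| 9.3.1 and note l | 1 | 1, 3, 5 | 1, 3, 5 | 0, 2, 4 |
| 9.3.1 and note l | 2 | 2, 4, 6 | 1, 3, 5 | 1, 3, 5 |
| 8.11 | 1 | 2, 4, 6 | 2, 4, 6 | 1, 3, 5 |
| 8.11 | 2 | 2, 4, 6 | 1, 3, 5 | 1, 3, 5 |

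Two results follow.

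1. The only on-treatment entry with at least one SL-401 cycle and no POM/DEX cycle is phase 1, Cycle 1 Day 1, under Section 9.3.1 and note l. Under Section 8.11 there is none: the first on-treatment draw in phase 1 follows one full combination cycle. For a patient who continues past the Run-in, the count of dedicated draws in that window goes from 1 to 0. Section 9.3.1 lists the draw among pre-infusion procedures; the count assumes that it also precedes that day's first POM/DEX dose.
2. Counted in SL-401 cycles, the phase-specific schedule lines the phases up at 1, 3 and 5. Section 8.11 gives 2, 4 and 6 in phase 1 against 1, 3 and 5 in phase 2.

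**Other samples in the same window**
- Section 8.13: immunogenicity serum at Run-in Day 5 and on Day 1 of each later cycle, before infusion. Leftover serum or plasma may be used for other markers such as IL-3, if the sponsor or investigator thinks it appropriate.
- Section 8.12: PK plasma with Run-in infusions 1 and 5.
- Section 9.5: correlative blood at EOT, which for a patient who stops during the Run-in comes before any POM/DEX.

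None of these gives whole blood for flow cytometry in a patient who goes on to Cycle 1.

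**Marrow instructions side by side**

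| Place | Post-baseline correlative marrow |
|---|---|
| Section 8.11 | During and after therapy |
| Table 13 note k | Specimens obtained to confirm response; none assigned from the end-of-therapy aspirate |
| Synopsis | Any aspirate left over from tumor assessment |
| Table 13 grid | Aspiration and biopsy row marked at EOT |
| Section 9.5 | Aspiration at EOT; correlative use not mentioned |

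The end-of-therapy aspirate is scheduled in note k, the grid and Section 9.5. The gap is that note k's correlative clause does not reach it.

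**The case against.** **Section 8.11 is outnumbered.** The visit list and the Schedule of Events agree with each other, and a site may well follow them. That makes the loss a risk rather than a certainty, but it does not remove the contradiction.

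**Nothing names Cycle 1 Day 1 as a single-agent comparison.** True; its value is inferred from the sequence of treatment. Each Run-in infusion is also preceded by methylprednisolone (Section 7.3.2.2), so the sample reflects SL-401 with steroid premedication, not SL-401 alone. It is still the only dedicated draw free of POM/DEX.

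**Phase alignment cuts both ways.** Counted in POM/DEX cycles, Section 8.11 is the schedule that matches the phases (1, 3, 5 in both). The misalignment argument holds for SL-401 exposure only and is secondary to the lost draw.

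**Other blood exists.** A reader might infer that under Section 8.11 no blood at all reflects SL-401 before POM/DEX. The documents do not support that: immunogenicity serum is drawn in the window and may be used for markers such as IL-3. That use is optional, depends on leftovers, and does not supply whole blood for flow cytometry.

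**Marrow.** A reader might infer from note k that all later marrow is limited to suspected responders. The note itself requires an end-of-therapy aspirate, its correlative clause does not say that its list is exhaustive, and the synopsis admits leftover aspirate from anyone. What stands is that the instructions differ, and note k leaves the end-of-therapy specimen out of its correlative clause. The choice of marrow comparison belongs to the separate translational analysis plan (Section 11.7).

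**Conclusion.** The blood schedules contradict each other for phase 1, and the difference has a consequence. For each phase 1 patient who continues past the Run-in, following Section 8.11 means no dedicated correlative draw, instead of one, after single-agent SL-401 with its premedication and before POM/DEX. Sampling in SL-401 cycles also falls out of step with phase 2. The planned phase 1 size of at most 18 is a ceiling on the number affected, because patients with a DLT in the Run-in are discontinued and never reach Cycle 1. Phase 2 cannot supply the missing sample, having no Run-in.

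The marrow point is smaller: an inconsistency in which post-baseline specimens yield correlative material. No count of affected patients is given, because the protocol states no CR rate from which to derive one.

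Both points concern exploratory objectives only. No primary or secondary endpoint, safety rule or sample-size figure depends on them. Correction is worthwhile because it is cheap and a missed draw is irrecoverable.

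**What to change.** 1. **Section 8.11, blood.** Replace the single schedule, for whole blood and for serum/plasma, with that of Section 9.3.1 and Table 13 note l: baseline; Day 1 of Cycles 1, 3 and 5 in phase 1; Day 1 of Cycles 2, 4 and 6 in phase 2; and EOT. State that the phase 1 Cycle 1 Day 1 sample is taken before the first POM/DEX dose. Cost: wording only, with five draws per patient as before.
2. **Table 13 note k, marrow.** Add that correlative material is also kept from the end-of-therapy aspirate already scheduled, so that the note agrees with Section 8.11 and the synopsis. Cost: an extra aliquot and its laboratory processing, with no added procedure. An aspirate aliquot does not supply the biopsy immunohistochemistry named in Section 4.3, so the amendment should also say whether an end-of-therapy biopsy is intended: the Table 13 grid implies one, while Section 9.5 lists aspiration only.
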